Statistical analysis of RNA-Seq expression data derived from samples of the treatment arms will be carried out in the R environment for statistical computing (RDC, 2016). In order to identify differentially expressed genes between the conditions, we will make use voom-limma framework (Ritchie et al., 2015). Briefly, linear models are fit for each gene to estimate the coefficients (= effect size) and their standard error. Empirical Bayes-moderated t-statistics and their associated p-values are then used to assess the significance of the observed expression changes.

In order to evaluate concerted differences of biologically related genes, single sample gene set enrichment will be employed via the GSVA R package (Hanzelmann, Castelo, & Guinney, 2013) which produces a gene-set by sample matrix with approximately normally distributed enrichment scores which can then be compared between treatment arms using for example linear models. Detailed statistical plan is as described in the manuscript [[name], submitted].

Columbia University Irving Medical Center
Herbert Irving Comprehensive Cancer Center
AAAS4165_Version Date: 07/07/2021

4.1.2 Phase 2

The phase 2 portion of the study will be amended after preliminary safety and efficacy results from phase 1 and other ongoing clinical trials have been analyzed and a summary incorporated within the protocol as an amendment including a rationale of the cohorts to be tested. The amendment will be submitted to the Scientific Review Committee (PRMC) and Institutional Review Board (IRB) at CUIMC for approval prior to activation of phase 2 portion of the study.

Three separate phase 2 studies will be conducted based on the differences in baseline response rate by disease subtype:

Cohort 1 – Advanced Pancreas Adenocarcinoma

Cohort 2 – Advanced Colorectal Adenocarcinoma

Cohort 3 – Histology Agnostic Adenocarcinoma

The primary outcome measure is best objective response by 16 weeks; that is, patients who achieve CR or PR within the first 16 weeks will be considered responders. Tumor response will be assessed by CT scans performed every 8 weeks using the Immune-Modified Response Evaluation Criteria in Solid Tumors (IM RECIST). We will use a Simon optimal 2-stage design for each disease subtype to allow for early stopping.

Advanced Pancreas Adenocarcinoma

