5. SUBJECT SELECTION AND WITHDRAWL

Each of the criteria in the following section must be met in order for a patient to be considered eligible for participation.

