5.1 Inclusion Criteria

For *Phase 1 and 2*, participants must have histologically confirmed KRAS-mutant malignancy that is metastatic or unresectable, and for which standard curative or meaningful life prolonging palliative measures do not exist or are no longer effective as described below (#3). Subjects with pancreas adenocarcinoma or colorectal adenocarcinoma have specific requirements. **At least 12 of the 18 evaluable patients within phase 1 should carry an active diagnosis of either pancreas or colorectal adenocarcinoma.**

Specific inclusion criteria are:

1. Histological or pathological confirmation of malignancy with a KRAS-activating mutation.

Cytologic or histologic proof of malignancy needs to be verified by the treating institution pathologist, either from the initial diagnostic biopsy or from the required pre-treatment biopsy, prior to initiation of any study-related therapy. Tumor must contain an activating KRAS mutation as determined by an FDA or New York State approved non-significant risk assay (within exons 2, 3, and 4). Subjects may be enrolled using prior *KRAS* positive result by non-FDA or New York State approved assay obtained per standard of care, but may not initiate treatment until *KRAS* mutation is confirmed by an FDA or New York State approved assay. FDA approved mutational analysis tests performed on blood which identify a KRAS mutation along with a biopsy which confirms tumor histology will be sufficient to meet this criteria. Please note, there is specific interest in KRAS G12R mutated patients with pancreas cancer or colorectal cancer.

2. Extent of disease

Advanced disease for which no curable options are available, including but not limited to, surgery, radiation, or loco-regional therapy. Subjects who are not deemed candidates for these curative therapies will be eligible if they meet other criteria.

3. Prior treatments

• Pancreas adenocarcinoma

Subjects must have progressed on or be intolerant of combination therapy containing either 5-Fluorouracil/Capecitabine- and/or gemcitabine-based therapy. Subjects who experienced disease recurrence while receiving adjuvant chemotherapy or within three months of completing adjuvant chemotherapy are eligible.

• Colorectal adenocarcinoma

Subjects must have progressed on or be intolerant of combination therapy containing 5-Fluorouracil/Capecitabine, and must have received Oxaliplatin and Irinotecan.

• MSI-H/dMMR or NTRK-fusion positive tumors

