Subjects must have received prior treatment with approved drugs for tumors harboring these aberrations.

• Histology agnostic cancers other than pancreas and colorectal adenocarcinoma (see above; Phase 1 and 2)

Subjects must have progressed on or be intolerant of all standard of care therapies that result in a median progression free survival benefit of ≥ 8 weeks, or overall response rate of $>5\%$.

Columbia University Irving Medical Center
Herbert Irving Comprehensive Cancer Center
AAAS4165_Version Date: 07/07/2021

4. ECOG performance status of 0 or 1
5. Age \geq 18 years
6. Adequate hematological and end-organ function (test results from within 14 days prior to initiation of study treatment):
 - ANC $\geq 1.5 \times 10^9/L$ without granulocyte colony-stimulating factor support
 - WBC count $\geq 2.5 \times 10^9/L$ (2500/ μL)
 - Lymphocyte count $\geq 0.5 \times 10^9/L$ (500/ μL)
 - Platelet count $\geq 100 \times 10^9/L$ (100,000/ μL) without transfusion
 - Hgb $> 9.0 \text{ g/dL}$
 - AST, ALT, and alkaline phosphatase (ALP) $\leq 2.5X$ upper limit of normal (ULN), unless elevated secondary to biliary obstruction from the pancreas mass and amenable to decompression prior to initiation of therapy
 - Serum total bilirubin $\leq 1.5X$ ULN, unless in patients with known Gilbert disease ($\leq 3X$ ULN), or unless elevated secondary to biliary obstruction from the pancreas mass and amenable to decompression prior to administration of investigational therapy
 - Albumin $\geq 3.0\text{g/dL}$
 - Creatinine within ULN or calculated creatinine clearance (CrCl) $>50 \text{ mL/min}$ using the Cockcroft-Gault formula
 - INR and aPTT $\leq 1.5X$ ULN except for those who are on stable anticoagulation for at least three months.
7. Measurable disease according to IM-RECIST and tumor accessible for fresh biopsy if ten adequate paired biopsied specimens have not been procured (Phase 1)
8. Negative pregnancy test

Women of childbearing potential must have a negative serum pregnancy test at screening and must agree to use an effective form of contraception from the time of the negative pregnancy test until a minimum of 3 months after the last dose of study drug. Effective forms of contraception include abstinence, hormonal contraceptive (injectable or implantable) in conjunction with a barrier method, or a double barrier method. Women of non-child-bearing potential must have been postmenopausal for ≥ 1 year or surgically sterile.

9. Birth control agreement

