23. Grade \geq 3 hemorrhage or bleeding event within 28 days prior to initiation of study treatment

24. Prior autologous stem cell, allogeneic stem cell, or solid organ transplantation

25. History of malignancy

Patient may not have a history of malignancy other than PDA within 2 years prior to screening, with the exception of those with a negligible risk of metastasis or death (e.g., 5-year overall survival of $> 90\%$), such as adequately treated carcinoma *in situ* of the cervix, non-melanoma skin carcinoma, localized prostate cancer, ductal carcinoma *in situ*, or Stage I uterine cancer.

26. Recent vaccination

Patients may not have been treated with a live, attenuated vaccine within 4 weeks prior to initiation of study treatment, or anticipate the need for such a vaccine during treatment with atezolizumab or within 5 months after the last dose of atezolizumab.

27. History of severe allergic anaphylactic reactions to chimeric or humanized antibodies or fusion proteins

28. Known allergy or hypersensitivity to 4-aminoquinoline compounds or any of the study drug excipients

29. Recent immunosuppressive treatment

Patients may not have been treated with systemic immunosuppressive medication (including, but not limited to, corticosteroids, cyclophosphamide, azathioprine, methotrexate, thalidomide, and anti-tumor necrosis factor alpha agents) within 2 weeks prior to initiation of study treatment, or

Columbia University Irving Medical Center
Herbert Irving Comprehensive Cancer Center
AAAS4165_Version Date: 07/07/2021

anticipate the need for systemic immunosuppressive medication during the course of the study, with the following exceptions:

- Patients who received mineralocorticoids (e.g., fludrocortisone), corticosteroids for chronic obstructive pulmonary disease or asthma, or low-dose corticosteroids for orthostatic hypotension or adrenal insufficiency are eligible for the study if receiving equivalent to < 10mg of prednisone daily.
- Patients who received a one-time pulse dose of systemic immunosuppressant medication are eligible for the study after approval from the Principal Investigator.

30. Inability to swallow medication or malabsorption condition that would alter the absorption of orally administered medications

31. History of retinal pathology

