The Affiliate site **must** submit a prospective deviation request to the CUMC lead PI for review and submission to the HICCC DSMC and CUMC IRB. Approvals must be obtained from all entities prior to implementation at the Affiliate site. If a prospective protocol deviation request is submitted for review (from an Affiliate site), the PI/site memo(s), HICCC DSMC approval(s) and correspondence and CUMC IRB deviation approval letter(s) should be forwarded to the Affiliate site for documentation. The Affiliate site is also required to obtain prospective local IRB approval as per institutional policies/procedures prior to implementing the proposed deviation. All documents and determinations must be clearly documented in the study patient’s medical record, research chart, and regulatory binder, as described.

The HICCC DSMC and PRMC will no longer accept eligibility deviations, but will still continue to accept deviations not related to eligibility.

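### Exclusion 25 exempts only pancreatic adenocarcinoma from the recent-malignancy bar, so read literally it conflicts with the sections that admit colorectal and other KRAS-mutant patients

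*Combined protocol and SAP*

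**What the plan says.** Section 5.2, item 25, reads: "Patient may not have a history of malignancy other than PDA within 2 years prior to screening". It continues "with the exception of those with a negligible risk of metastasis or death" and gives examples such as treated in situ or early-stage cancers. The protocol uses PDA for pancreatic adenocarcinoma. Item 25 does not exempt the cancer under study, and it is not limited to one phase.

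The intended population is wider:

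- Section 5.1, for both phases: "participants must have histologically confirmed KRAS-mutant malignancy that is metastatic or unresectable".
- Section 5.1, on the Phase 1 mix: "At least 12 of the 18 evaluable patients within phase 1 should carry an active diagnosis of either pancreas or colorectal adenocarcinoma".
- Section 5.1, item 3, sets prior-treatment rules for colorectal adenocarcinoma and separately for "Histology agnostic cancers other than pancreas and colorectal adenocarcinoma".
- Section 4.1.2 plans three Phase 2 studies, including "Cohort 2 – Advanced Colorectal Adenocarcinoma" and a histology-agnostic cohort.

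On the force of the criteria, section 5 states: "Each of the criteria in the following section must be met in order for a patient to be considered eligible for participation". Section 6.1 has a central registrar verify eligibility against a signed checklist and source documents before therapy starts, and section 17.5 does the same for affiliate sites. Section 5.5.1 removes a patient later found not to meet key eligibility criteria.

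On departures from eligibility the protocol gives two answers. Section 17.6, on affiliate sites, states: "The HICCC DSMC and PRMC will no longer accept eligibility deviations". Section 13.3 lists eligibility waivers among the items that go to the DSMC for approval.

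**The concern.** A patient enrolled for metastatic colorectal cancer has, at screening, a malignancy that is not PDA. The same holds for every patient in the histology-agnostic group. Item 25 as worded therefore excludes patients whom sections 4.1.2 and 5.1 set out to recruit.

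What is at stake is the eligibility record. A registrar or monitor applying the text must either refuse such patients or accept them against a mandatory criterion. If they are accepted, each non-pancreas patient can be cited as an eligibility departure. The result could be inconsistent handling between sites, or an argument over who belongs in the evaluable set when the data are reviewed.

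**Working it through.** No statistical figure in the plan is in dispute. The check is a reading of the text followed by a count.

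**Step 1. Does the study cancer fall within item 25?** Take a patient with advanced KRAS-mutant colorectal cancer.

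- *Is it a malignancy other than PDA?* Yes.
- *Is it within 2 years before screening?* Yes. The disease is present at screening, whenever it was first diagnosed.
- *Does the negligible-risk exception apply?* No. Section 5.1 requires disease that is metastatic or unresectable.
- *Is there another exemption?* None was found in the documents.

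The patient meets section 5.1 and fails item 25. The same steps apply to the histology-agnostic group, which section 5.1 defines so as to leave pancreas out.

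**Step 2. Does the wording work as a second-cancer rule?** Not for these patients. Take a colorectal patient with a separate pancreatic adenocarcinoma in the past 2 years. Item 25 does not count that second cancer, because PDA is the exempt diagnosis. For non-pancreas patients the wording therefore catches the study cancer and misses one possible second cancer.

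**Step 3. Reproduce the planned totals.** The synopsis gives the cohort ranges as pancreas 23–67, colorectal 20–34 and histology-agnostic 23–56.

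- Maximum: 67 + 34 + 56 = 157.
- Minimum, all cohorts stopping at stage 1: 23 + 20 + 23 = 66.

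Both agree with sections 4.1.2.1 and 4.2.

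**Step 4. Count the Phase 2 patients affected.** Affected patients = colorectal + histology-agnostic.

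| Case | Affected | Total | Share |
|---|---|---|---|
| All cohorts stop at stage 1 | 20 + 23 = 43 | 66 | 65% |
| All cohorts completed | 34 + 56 = 90 | 157 | 57% |
| Only pancreas continues | 20 + 23 = 43 | 67 + 43 = 110 | 39% |
| Only pancreas stops | 34 + 56 = 90 | 23 + 90 = 113 | 80% |

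The count runs from 43 to 90. The share also depends on whether the pancreas cohort continues, as the last two rows show.

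**Step 5. Count the Phase 1 patients affected.** Section 5.1 asks for at least 12 of 18 with pancreas or colorectal cancer, which leaves up to 18 − 12 = 6 places for other histologies. It sets no split between pancreas and colorectal. The affected number can therefore be anything from 0 (all 18 pancreas) to 18 (for example 12 colorectal and 6 other).

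**The case against.** The strongest reply is that nobody would apply item 25 to the study cancer. Its heading concerns history, its examples are typical prior or coexisting second cancers, and section 5.1 describes the study cancer as an active diagnosis. Sections 4.1.2 and 5.1 admit colorectal and other histologies by name, with their own treatment rules and sample sizes. Read as a whole, the protocol contains a second-malignancy exclusion with a stray disease name. This stands as a statement of intent. A reader might otherwise infer that Cohorts 2 and 3 cannot enrol and that Phase 1 is confined to pancreas. That follows only if section 5.1 is set aside, so the documents do not support it. The reply does not cure the text, however: PDA is the one study cancer named as exempt, and every criterion is mandatory.

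A second reply is that Phase 2 must be amended, and the amendment approved, before it opens (sections 1 and 4.1.2), so no Cohort 2 or 3 patient is affected today. This stands too, and the Phase 2 counts are conditional on the wording surviving. But the described amendment concerns Phase 1 results and the rationale for the cohorts. It does not mention eligibility wording, and item 25 already governs Phase 1.

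A third reply is that a waiver could be granted. A reader of section 17.6 alone might conclude that none is possible, but section 13.3 refers to eligibility waivers approved by the DSMC. The documents conflict, and neither answer can be taken as settled.

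Two limits remain. The eligibility checklist is not among the documents, so how it words item 25 is unknown. A reader might also infer that the criterion was carried over from a pancreas-only study. Other pancreas-specific phrases make that plausible, but the documents do not say so.

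**Conclusion.** The concern holds as an internal inconsistency. Item 25 as written contradicts sections 4.1.2 and 5.1 for every patient whose study cancer is not pancreatic adenocarcinoma. It is not a design choice to exclude those patients, and it touches no endpoint, error rate, sample size or analysis.

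The present exposure is the non-pancreas patients among the 18 in Phase 1. The Phase 2 exposure, 43 of 66 up to 90 of 157, assumes that item 25 passes unchanged through the planned amendment. Quoting 57% of Phase 2 as already affected would overstate the matter, since that is the case in which every cohort is completed, in a phase not yet open.

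The practical risk is uneven registration decisions and avoidable audit findings. It is worth correcting because the rule is operative and waivers are not a reliable remedy.

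**What to change.** In item 25, replace the words *other than PDA* with *other than the malignancy under study*, and leave the listed exceptions unchanged. Check the eligibility checklist against the new wording so that item 25 agrees with sections 4.1.2 and 5.1. In the same amendment, reconcile sections 13.3 and 17.6 on whether eligibility waivers are accepted.

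Make the change now and not with the Phase 2 amendment, because Phase 1 is already governed by item 25. The cost is one phrase in item 25, the reconciling sentence and the usual approval. Planned numbers stay at 18 in Phase 1 and 66 to 157 in Phase 2.

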5.3 Inclusion of Women and Minorities

Both men and women of all races and ethnic groups are eligible for this trial. See Table 3 below for specific accrual targets.

Table 3. Accrual Targets

| Ethnic Category | Sex/Gender | | | | Total |
|------------------------|-------------------|----------|--------------|----------|--------------|
| | Females | | Males | | |
| Hispanic or Latino | 2 | + | 2 | = | 4 |
| Not Hispanic or Latino | 5 | + | 9 | = | 14 |
| TOTAL | 7 | + | 11 | = | 18 |
| Racial Category | | | | | |

**Columbia University Irving Medical Center
Herbert Irving Comprehensive Cancer Center
AAAS4165 Version Date: 07/07/2021**

| | | | | | |
|---|-----------|---|-----------|---|-----------|
| American Indian or Alaskan Native | 0 | + | 0 | = | 0 |
| Asian | 0 | + | 0 | = | 0 |
| Black or African American | 1 | + | 1 | = | 2 |
| Native Hawaiian or other Pacific Islander | 0 | + | 0 | = | 0 |
| White | 6 | + | 10 | = | 16 |
| TOTAL | 7 | + | 11 | = | 18 |
| | (A1 = A2) | | (B1 = B2) | | (C1 = C2) |

5.4 Subject Recruitment

Patients will be recruited for the study from investigator or co-investigator clinical practices and referring physicians.

5.5 Early Withdrawal of Subjects

5.5.1 When and How to Withdraw Subjects

- If at any time the patient develops progressive disease, he/she will be taken off treatment and referred for alternative therapy.
- If at any time the patient develops unacceptable toxicity, he/she will be removed from study treatment.
- If at any time the patient is found to not meet key eligibility Criteria for Patient/Subject Eligibility (e.g., a change in diagnosis), the patient will be removed from study.
- If the patient fails to comply with the defined treatment plan and follow-up evaluations, the patient will be removed from the study treatment.
- If the patient withdraws consent for continued participation, he/she will be removed from study treatment. Patient may agree to be contacted for follow up data.

5.5.2 Data Collection and Follow-up for Withdrawn Subjects

If a patient withdraws consent to participate in the study treatment administration, every attempt will be made to follow up for survival data.

6. REGISTRATION PROCEDURES

6.1 CUIMC Research Participant Registration

All participants must be centrally registered through the Central Registration Office within Herbert Irving Comprehensive Cancer Center at CUMC prior to initiation of study treatment.

Registration hours are available Monday through Friday from 9:00am – 5:00pm EST (excluding holidays and weekends). Same-day subject registrations (and after hour registrations) will be accommodated on a case-by-case basis, provided that the study team has expressed all time sensitive registration concerns/cases in a timely manner to the Central Registration Office.

The following requirements exist for participant registration:

- Confirm eligibility, as defined in the section entitled Criteria for Subject Eligibility.
- Obtain informed consent by following procedures defined in section entitled Informed Consent Procedures, along with applicable institutional policies and federal regulations.
- Only Investigators/Research personnel properly trained and delegated to consent subjects for this protocol will participate in the consenting process. Furthermore, properly delegated/trained Physician Investigators (e.g., MD, MD PhD) are required to sign/verify a protocol specific Eligibility Checklist for each subject enrolled on the study, in addition to providing the relevant source documentation confirmation subject eligibility.

CPDM Central Registration Procedures:

Within 48 hours of obtaining consent (excluding holidays and weekends), a completed/signed IRB-approved informed consent HIPAA form, and demographics forms must be submitted to the CPDM Central Registration Office via an email to [contact] or fax to [contact], with the subject line “AAAS4165 Pending Subject Registration Request (PHI)”. Upon receipt, applicable subject information as well as a “pending eligibility” status will be entered into HICCC’s institutional database. This status will remain until further source documentation is made available to confirm overall patient eligibility. Required materials for all pending registration submissions are as follows:

- Completed/signed IRB approved/stamped Informed Consent Forms, including additional study ICFs (e.g., tissue, DNA, etc.), as applicable.
- The completed/signed IRB approved HIPAA Authorization form
- Completed/signed CPDM ICF checklist
- Completed/signed HICCC personal census form
- Completed/signed CPDM Demographics Note to File

Columbia University Irving Medical Center
Herbert Irving Comprehensive Cancer Center
AAAS4165_Version Date: 07/07/2021

In order to confirm eligibility status, Investigators/designees (e.g., study specific Clinical Research Coordinator/Research Nurse, etc.) must submit the following documentation to the Central Registration Office via email or fax:

- Completed/signed study-specific Eligibility Checklist (signed by Physician level Investigator)
- Copies of source documentation necessary for each item to be verified on the CPDM specific Eligibility Checklist, including but not limited to:
 - Copy of required laboratory test and procedure reports (e.g., hematology, serum chemistry, pregnancy test when applicable, MRI reports, CT/bone scans, etc.)
 - Copy of pathology and surgical reports
 - Copy of clinic note(s) or other appropriate medical records capturing the consent process information, along with providing source documentation of any other items needed for screening/eligibility that are not captured in other source document forms (e.g., positive investigator statements of unique eligibility items not captured via other direct source documentation, concomitant medication lists, etc.)

Subject line of email or fax should read: “AAAS4165 Complete Subject Registration Request (PHI)”.

Upon receipt of documentation, participant eligibility information will be verified by a qualified Central Registration Registrar. If any questions arise during the review process, email queries to the applicable study team personnel for clarification prior to enrollment. All applicable finalized registration/eligibility information will then be entered into HICCC’s institutional CTMS database by the Central Registration Registrar. Upon completion, an official subject registration notification email will be sent to the PI/research team to include eligibility/enrollment status and subject ID information. Protocol therapy may not be initiated prior to receipt of this notification.

All screen fail/ineligible subjects, as well as subject’s who withdraw consent prior to enrollment/initiation of protocol therapy must be submitted to the Central Registration office in a manner analogous to the procedures noted above. Applicable source documentation will be required within the corresponding submissions.

